Developing a brief early cognitive intervention for PTSD and alcohol misuse

NCT02808468

03/08/2014

Study Protocol

This study is a small pilot randomized controlled trial (RCT) to test initial efficacy of a one session + four coaching call cognitive intervention compared to symptom monitoring for the reduction of PTSD and alcohol use following a recent sexual assault (SA). Participants will be assessed at baseline, randomly assigned to receive the intervention plus weekly assessments vs. weekly assessments only (AO), and assessed again at 3-month follow-up.

Recruitment and Participants: Participants are recruited via community advertisements (flyers, online) and specific outreach targeted toward female identifying students enrolled at the first author's institution. We will collaborated with local community organizations to receive referrals.

Participants will be 76 (n = 38 intervention, n = 38 AO) women who are 2-10 weeks post SA and report alcohol misuse and PTSD symptoms. We will restrict our sample to women given that the majority of SA victims are female and the pilot nature of this study. For this research, SA will be defined as any non-consensual sexual activity ranging from forced penetration to unwanted contact. Participants will need a minimum of subthreshold PTSD symptoms related to recent SA (specifically criteria for two of the three PTSD symptom clusters; 1 reexperiencing, 3 avoidance, 2 hyperarousal) to ensure that they are experiencing SA related distress. Participants will endorse hazardous drinking over the past month, defined as exceeding NIAAA recommendations for low risk drinking for women (more than 3 drinks on one occasion) and at least two negative consequences of drinking. Additional inclusion criteria include: 1) female gender; 2) age \geq 18 years, 3) capacity for informed consent, 4) English fluency, 5) no planned absences that would interfere with 5 weeks of participation, and 6) access to a telephone. Individuals will be excluded if they are 1) acutely suicidal with intent/plan or 2) exhibit current

psychosis.

Measures. Below is a description of measures for each time point. Phone Screening. To initially assess for SA exposure, we will include 2 questions on nature and timing of assault. We will also include a 20-item PTSD screen to assess that participants meet at minimum subthreshold PTSD symptoms. Finally, we will ask 2 items that assess quantity and frequency of drinking, and one to determine if alcohol has caused any problems in the previous week to ensure likelihood of hazardous drinking. *Interview Measures*. At baseline interviews are administered including the mood and psychotic disorder modules of the Structured Clinical Interview for DSM-IV (SCID) at baseline to assess for exclusion criteria of current psychosis or acute suicidality. At baseline and 3-month follow-up, we will administer the Timeline Followback (TLFB), a calendar based assessment of drinking with established reliability, to assess for quantity and frequency of alcohol use for the prior month. This will enable us to assess drinking at baseline and change in drinking following the intervention. Finally, at baseline and 3month follow-up we will administer the Posttraumatic Stress Symptom Scale- Interview version (PSS-I) to assess for both DSM-IV diagnostic criteria of PTSD and severity of symptoms over the past two weeks. The PSS-I has excellent reliability and validity and will assess for change in PTSD symptoms with the intervention. Self-report Measures. We will administer self-report measures of drinking, assault history, and psychopathology at the in-person baseline and 3month assessments and a briefer subset of these measures will be administered online at weekly intervals for four weeks following baseline. All self-report measures are widely used and have established reliability and validity. Constructs that are assessed include demographic information to describe the sample (e.g., age, race), history of unwanted sexual experiences, alcohol measures at baseline, weekly assessments, and 3-month follow-up to assess drinking behavior,

the Drinking Inventory of Consequences (DrInC) to assess interpersonal, physical, social, impulsive, and intrapersonal consequences of alcohol use, and the Daily Drinking Questionnaire (DDQ) to assess quantity/frequency of alcohol use over the previous week to look at self-report changes in drinking. Similarly, at baseline, weekly and follow-up we will administer the Posttraumatic Diagnostic Scale (PDS) to assess for ongoing PTSD symptoms and change in PTSD symptoms. Finally, at baseline and 3-months we will administer self-report measures to assess functioning and change in functioning including drug use, depression, and treatment received. Finally, a post-study reactions questionnaire will be given at the last weekly intervention session to assess participant reactions to the assessment and intervention strategies. This measure will be used to assess the feasibility and acceptability of the intervention.

Assessment and Intervention Training: Study assessors will be trained to administer interview assessments of PTSD and alcohol use and self-report measures, by receiving group didactics on interview measures and doing role plays of conducting interview assessments. They will complete at least one mock assessment before beginning assessments. The assessors will meet weekly as a group to discuss and make inclusion decisions and minimize rater drift and will receive as-needed supervision on assessment techniques. Interventionists will also be trained in the 90-minute in-person intervention and coaching calls. Intervention training will consist of group didactics, role plays, and mock interventions. Interventionists will participate in ongoing weekly group supervision. Fidelity to the intervention and reliability of assessments will be calculated for a subset of the sample once data collection is complete.

Procedures: Study procedures will begin with phone screening with the research coordinator (RC) to determine initial eligibility for SA exposure, PTSD symptoms, and alcohol use.

Potentially eligible individuals will be scheduled for an in-person baseline session.

This study involves 7 assessment time-points: baseline, at intervention or post-randomization (for the AO group), 4 weekly assessments, and 3-month follow-up assessment. The baseline session will last 1.5-2 hours and will consist of interview (PSS-I, TLFB, SCID modules) and self-report measures on SA (SES), PTSD (PDS), depression/suicide (BDI), and substance use (DDQ, DrInC, DUDIT,). Baseline will be conducted by an assessor, and at the conclusion the RC will inform the participant of randomization condition (intervention vs. AO). Participants will be randomized with their condition known only to the RC and the PI, while the assessor who conducts baseline assessments will remain masked to condition. At baseline participants will be compensated at a rate of \$20/hour. One week after baseline, individuals randomized to the intervention will return and meet with a interventionist for a 90 minute in-person intervention. At that time they will complete self-report measures on drinking and PTSD and will be compensated \$10 for completing the questionnaires (PDS, DDQ, DrInC). One week following baseline AO participants will log on to a secure web server, complete these same measures of PTSD and drinking behavior, and be compensated \$10. For the next 4 weeks, intervention participants will complete weekly 15-minute coaching calls with their assigned interventionist. Prior to each coaching call they will be prompted to complete on-line self-report measures of PTSD and alcohol use (PDS, DDQ, DrInC). AO participants will complete these same measures weekly without the coaching call. Participants will receive \$10 for each on-line assessment they complete; those who complete all 4 will receive a \$20 bonus. Finally, participants will be assessed at 3-month follow-up. They will meet with the same assessor from baseline and will recomplete interviews of PTSD and alcohol use, and self-report measures of alcohol and drug use, PTSD, depression, treatment satisfaction (reaction to treatment) and treatment received (Form 90). At 3-month follow-up participants will be paid \$25/hour.

Participant Retention. We will use strategies including reminder calls/texts, weekly check in calls during active treatment for both groups, increasing incentives for follow-ups, and bonus payments for full completion to achieve an expected 80% retention rate.

Power and Data Analytic Plan.

Data analytic plan. Prior to inferential statistics, scale scores will be calculated for each of the variables following previously validated procedures. Univariate and bivariate descriptive statistics will be used to assess distributions and simple relationships among study variables. We will examine factors such as completion rate, number and length of coaching calls completed, and participants' reaction to treatment (reaction to treatment) to examine the feasibility of the intervention.

Preliminary Analyses

Stata 15.1 (StataCorp, 2017) was used for all analyses. Potential differences by treatment condition in demographics and background characteristics including age, race, ethnicity, sexual orientation, and treatment history were examined with *t*-tests or chi-square tests.

Primary Analyses

First, we will examine intervention satisfaction and acceptability by means and standard deviations of each satisfaction rating. Next, to evaluate differences between BRITE and the symptom monitoring control condition in PTSD and alcohol use outcomes between baseline and 3-month follow-up, we will conduct separate multilevel mixed-effects models for PTSD symptom severity, average drinks per drinking day, heavy episodic drinking frequency, and alcohol consequences. We will fit two-level random-intercept models with an independent covariance structure between the random effects controlling for treatment history testing for a condition x time interaction. We will conduct similar multilevel mixed-effects models examining

differences between BRITE and AO in PTSD symptom severity, average drinks per drinking day, and heavy episodic drinking frequency using self-reports at baseline, randomization (also intervention delivery session), each of the four weeks of coaching calls, and the 3-month follow-up controlling for treatment history. Pairwise comparisons for intervention x time effects were examined as described above.

Missing data. For missing data, we will examine both intent-to-treat and completer analyses to examine possible differences in the outcome as a result of drop out. For missing data due to a participant providing incomplete data, we will examine whether the missingness can be considered ignorable (e.g., missing completely at random or related to variables in the analyses [including earlier time points]). For any non-ignorable missing data, we will use multiple imputation procedures or employ analytic procedures that handle missing data in less biased ways such as maximum likelihood estimation.

Power analysis. The RCT was powered to examine the main hypothesis regarding the efficacy of the intervention compared to AO on PTSD and drinking. We expect a medium-to-large effect size for both alcohol and PTSD outcomes Using G*Power 3.1.7 with an ANOVA with 3 repeated measures, a sample size of 60 (30 per condition) is needed to identify medium-to-large effects with power of .80. To obtain this sample of treatment completers, we will recruit 76 women (38 per condition).

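### At week 1 the self-report setting differs by arm and its order relative to the session is unstated, yet the wave enters the seven-wave condition x time models as an ordinary time point

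*Combined protocol and SAP*

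**What the plan says.** The Procedures section describes the second of the seven assessment points separately for each arm.

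- Intervention arm: "One week after baseline, individuals randomized to the intervention will return and meet with a interventionist for a 90 minute in-person intervention". It continues: "At that time they will complete self-report measures on drinking and PTSD". The forms are the PDS, DDQ and DrInC.
- AO arm: "One week following baseline AO participants will log on to a secure web server, complete these same measures of PTSD and drinking behavior".

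For the four later weekly waves, the same section fixes both mode and order in the intervention arm: "Prior to each coaching call they will be prompted to complete on-line self-report measures". For the control arm it says "AO participants will complete these same measures weekly without the coaching call". The Measures section places the baseline and 3-month self-reports in person for everyone. It describes a shorter set given online each week for four weeks, which does not clearly cover the week-1 visit.

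Primary Analyses has two sets of mixed models. The first compares the arms between baseline and 3 months on four outcomes, including alcohol consequences. The second uses self-reports at all seven waves for PTSD severity, drinks per drinking day and heavy episodic drinking. Its second wave is labelled "randomization (also intervention delivery session". Pairwise intervention x time comparisons follow. The plan gives this wave no special handling.

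**The concern.** Week 1 is the only wave at which the stated procedure gives the two arms different settings. Baseline and 3 months are in person for both, and the four coaching-call weeks are online for both. A change from baseline to week 1 therefore crosses from in-person to web completion in the AO arm only. The next step, to the first coaching-call week, crosses that line in the intervention arm only.

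The forms ask about drinking and assault-related symptoms, where place and privacy can affect what is reported. If some intervention participants answer after the session, their immediate reaction to it is mixed in as well. The model cannot separate either influence from treatment, because each coincides with arm at that wave. An artefact would add to the condition x time interaction in the seven-wave models. It would also be tested directly in any pairwise comparison involving week 1.

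**Working it through.** **The plan's own figure.** The Power analysis gives 30 per condition and Participant Retention expects 80%. 30 / 0.80 = 37.5, rounded up to 38 per arm, and 2 x 38 = 76. The stated sample size reproduces. It does not bear on this point, except to supply 30 and 38 per arm as the two sizes to use below.

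**Where the setting differs.**

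| Wave | Intervention arm | AO arm |
|---|---|---|
| Baseline | in person | in person |
| Week 1 | at the intervention visit, order unstated | web |
| Four coaching-call weeks | web, before the call | web |
| 3 months | in person | in person |

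**What an artefact could do.** The documents give no size for a setting effect and no within-person correlation. Both are assumed here, with two-sided 5% tests, complete data, compound symmetry and no true treatment effect. A shift of d SD is placed at week 1 in one arm.

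*Week-1 contrast (change from baseline).* SE = sqrt(2(1 - rho) x 2/n), and the rejection probability is Phi(d/SE - 1.96) + Phi(-d/SE - 1.96). With rho = 0.6 and n = 30, SE = sqrt(0.8 x 2/30) = 0.231. At d = 0.2, d/SE = 0.866 and the probability is 13.9%. With n = 38, SE = 0.205.

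*Joint interaction test over seven waves.* Noncentral F with 6 numerator df, 6(2n - 2) denominator df and noncentrality (n/2) d^2 (6/7)/(1 - rho). The factor 6/7 arises because a shift at one wave of seven leaves d^2(1 - 1/7) after centring. At n = 30 and d = 0.2, noncentrality = 15 x 0.04 x 0.857/0.4 = 1.286 with 6 and 348 df, and the probability is 10.7%.

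Results at rho = 0.6:

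| Shift (SD) | Week-1 contrast, 30 / 38 per arm | Joint test, 30 / 38 per arm |
|---|---|---|
| 0.1 | 7.2% / 7.8% | 6.3% / 6.6% |
| 0.2 | 13.9% / 16.4% | 10.7% / 12.5% |
| 0.3 | 25.5% / 31.0% | 19.6% / 24.5% |

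Sensitivity to the correlation, joint test at 30 per arm, for shifts of 0.1, 0.2 and 0.3 SD: 6.0%, 9.4% and 16.2% at rho = 0.5; 6.7%, 12.9% and 25.6% at rho = 0.7.

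*Baseline to 3-month contrast.* This wave is not an input, so the shift from this source is zero.

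**The case against.** A fair defence would make five points.

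- **Timing.** A reader might infer that the arms are measured at different times. They are not: both are scheduled one week after baseline. Only the order of forms and session within the intervention visit is open, and the plan is silent on it rather than placing the forms afterwards. This stands.
- **Mode.** A reader might infer that the interventionist administers the forms. The text does not say so; they are self-report, and completing the same web form on site is not excluded. This stands, but the place would still differ by arm and the order would still be open.
- **Main efficacy result.** A reader might infer that the whole efficacy comparison is compromised. The baseline to 3-month models come first, cover all four outcomes and do not use week 1. Nor do the seven-wave models list alcohol consequences, so the DrInC collected at week 1 does not carry the problem into them. This stands and limits the reach.
- **Interpretation.** A lone arm difference at a wave labelled as randomization would hardly be read as efficacy, and the DDQ asks about the previous week, which lies almost wholly before the session. This weakens the argument about order for the drinking outcomes. It does not deal with setting, or with the joint interaction test, which absorbs a week-1 shift without showing where it arose.
- **Size.** The shift and the correlation are both assumed, and at 0.1 SD the error rates are close to nominal. This stands, so the figures are illustrations and not estimates.

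**Conclusion.** The point holds within limits. By the stated procedure, setting coincides with arm at week 1, the order relative to the session is not fixed, and the wave is modelled as if comparable. What is exposed is the seven-wave models for PTSD severity, drinks per drinking day and heavy episodic drinking, together with their pairwise comparisons.

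The true size is unknown. For shifts of 0.1 to 0.3 SD at correlation 0.6, the false-positive rate ranges from near nominal to roughly five times nominal for the week-1 contrast at 30 per arm, and to roughly four times nominal for the joint test. The rates are somewhat higher at 38 per arm. No direction of bias can be given. The change is worth making because it is cheap; the documents do not support a claim that the trial's baseline to 3-month comparison is biased by this wave.

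**What to change.** - **Procedure.** Have intervention participants complete the week-1 forms on the same web server before the session begins, as the plan already requires before each coaching call. For those who arrive without having done so, allow self-completion on site before the session as a back-up, and record the mode.
- **Analysis.** State that week 1 is a post-randomization, pre-intervention wave in the seven-wave models, so that an arm difference there is not read as an effect of the session. Participants learn their condition at the end of baseline, so a difference from knowing the allocation would remain possible.
- **If data are already collected.** Report the actual mode and order at week 1 and add a sensitivity analysis of the seven-wave models that omits the wave.

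Cost: a small procedural change using a web system and prompts that already exist. The downside is a small risk of missing week-1 forms in one arm only, which the on-site back-up is meant to limit. The sensitivity analysis needs no new data.

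### The primary condition x time test compares mean change between arms; it is valid, but a baseline-adjusted 3-month comparison would be more precise using data already collected

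*Combined protocol and SAP*

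**What the plan says.** The Primary Analyses section compares the arms on "PTSD and alcohol use outcomes between baseline and 3-month follow-up". Separate models cover PTSD severity, drinks per drinking day, frequency of heavy episodic drinking and alcohol consequences. They are "two-level random-intercept models with an independent covariance structure between the random effects", and the tested effect is specified as "controlling for treatment history testing for a condition x time interaction". Baseline is therefore one of the two outcome occasions, and treatment history is the only covariate. No link or distribution is stated for any outcome, and no section plans a baseline-adjusted 3-month comparison.

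Treatment history appears in Preliminary Analyses among "background characteristics including age, race, ethnicity, sexual orientation, and treatment history", but it is not defined. The self-report measures under Measures also assess "change in functioning including drug use, depression, and treatment received" at baseline and at 3 months.

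The interview measures of PTSD and drinking, and the alcohol self-reports, are taken at baseline and again at 3 months (Measures; Procedures). The participant learns her condition only at the end of the baseline session. Missing data states that "we will examine both intent-to-treat and completer analyses". Power analysis says the trial was sized for efficacy on PTSD and drinking, with 60 completers.

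**The concern.** With two occasions, a linear link and a condition main effect in the model, the condition x time coefficient is the difference between arms in mean change. This is exact in completers and approximate when baseline-only women stay in the likelihood.

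The contrast subtracts the whole of any chance baseline imbalance, when only the part that predicts follow-up should be removed. With 30 per arm, one standard error of imbalance is √(2/30) = .26 SD. At a correlation of .5 and equal SDs, the change contrast then over-corrects by (1 − .5) × .26 = .13 SD.

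The treatment-history adjustment does not help. An effect that is constant over time already cancels within each woman, and any difference in change by treatment history is left unadjusted.

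What is at stake is precision. In a trial of this size, described as powered for efficacy, a tighter estimate of the same effect is available without recruiting or measuring anyone further.

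**Working it through.** **The plan's own figure.** At 80% retention (Participant Retention), 30 / .80 = 37.5, rounded up to 38 per arm, or 76 in total. This matches. The 60 completers can be reproduced only with assumed inputs. For example, a between-groups repeated-measures F test with three measures, f = .30, correlation .5 and alpha .05 needs 62, and has power .799 at 60. That calculation is for three measures and not for the two-occasion model, so it does not give the power of the planned test.

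**Inputs from the documents.** 38 randomised and 30 completers per arm; two occasions.

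**Assumptions, none in the documents.** Two-sided alpha .05; linear link; SD 1 at both times unless stated; dropout unrelated to outcome; baseline to 3-month correlation ρ = .3, .5 or .7; true effect d = .5, .6 or .8 SD. The plan says only: "We expect a medium-to-large effect size for both alcohol and PTSD outcomes".

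**Variance per arm, in SD² units**

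- Planned, completers (mean change): 2(1 − ρ)/30
- Planned, intent-to-treat likelihood: (1 − ρ)²/38 + (1 − ρ²)/30
- Baseline-adjusted: (1 − ρ²)/30

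The completer ratio, adjusted to planned, is (1 − ρ²)/[2(1 − ρ)] = (1 + ρ)/2. At ρ = .5 the three variances are 1/30 = .0333, .25/38 + .75/30 = .0316 and .75/30 = .0250. The ratios are .0250/.0333 = .75 and .0250/.0316 = .79. The SE of the arm difference is √(2 × variance per arm).

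| ρ | SE planned, completers | SE planned, intent-to-treat | SE adjusted | Variance ratio, completers | Variance ratio, intent-to-treat |
|---|---|---|---|---|---|
| .3 | .306 | .294 | .246 | .65 | .70 |
| .5 | .258 | .251 | .224 | .75 | .79 |
| .7 | .200 | .197 | .184 | .85 | .88 |

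**Power** (noncentral t; 58 df planned, 57 df adjusted), planned to adjusted:

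| d | Analysis | ρ = .3 | ρ = .5 | ρ = .7 |
|---|---|---|---|---|
| .5 | Completers | .36 to .51 | .48 to .59 | .69 to .76 |
| .5 | Intent-to-treat | .39 to .51 | .50 to .59 | .70 to .76 |
| .6 | Completers | .49 to .67 | .63 to .75 | .84 to .89 |
| .6 | Intent-to-treat | .52 to .67 | .65 to .75 | .85 to .89 |
| .8 | Completers | .73 to .89 | .86 to .94 | .98 to .99 |
| .8 | Intent-to-treat | .76 to .89 | .88 to .94 | .98 to .99 |

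**Unequal SDs.** With k = follow-up SD / baseline SD, the completer ratio is k²(1 − ρ²)/(1 + k² − 2ρk). At ρ = .5 it is .57, .89 and .94 for k = .8, 1.25 and 1.4. At ρ = .7 and k = 1.4 it is 1.00, so there is no gain.

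**Identity with mean change.** On one complete simulated dataset of 60, the mixed-model interaction with a treatment-history covariate was −.28449 (SE .24768). The difference in mean change gave the same estimate and SE.

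**Simulation with dropout.** 76 women, 30 per arm retained at random, d = .6, treatment-history effect of .5 SD constant over time, 2,800 runs per ρ. The variance ratio of the constrained model (with treatment history x time) to the planned model was .71, .82 and .90 at ρ = .3, .5 and .7. Power went from .52 to .67, .66 to .76 and .86 to .89. Both models averaged −.59 to −.60 against a truth of −.60. Adding the treatment-history main effect to the planned model moved the interaction by only .016, .012 and .007 SD on average (maximum .096).

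**The case against.** The strongest reply is that nothing is wrong with the planned test. It is unbiased, and in simulation of the complete-data change-score test its null rejection rate was about 5%. The trial calls itself a small pilot, so choosing between two valid estimators may look like preference. That the test is valid is agreed. The point is efficiency, and it counts because the plan claims power for efficacy.

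Second, the size of the gain is assumed throughout. The power gain runs from about 18 points (ρ = .3, d = .6, completers) to about 1 point (ρ = .7, d = .8). Women are selected for symptoms and hazardous drinking, which could compress the baseline SD. At k = 1.25 the completer ratios become .78, .89 and .98 for ρ = .3, .5 and .7, and at 1.4 they become .84, .94 and 1.00. This stands as a limit on the benefit. Recovery could equally compress follow-up scores, and the documents do not settle the direction. In large samples the adjusted variance is never larger. Estimating the baseline slope costs a factor of about 1 + 1/56, or roughly 2%, at 60 completers.

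Third, the treatment history x time term may seem surplus. It only matches the free treatment-history coefficient that a 3-month regression would have.

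Fourth, the same section plans separate models over all seven occasions, and some of its wording is in the past tense. Neither removes the inefficiency in the two-occasion primary model. If outcome data have already been analysed, though, replacing the model would be a post hoc change.

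**Conclusion.** The point holds as a recommended improvement and not as an error. On a linear scale, with treatment history fixed at baseline, the planned test is a valid comparison of mean change. It gives up precision that baseline adjustment would recover.

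With equal SDs and correlations of .3 to .7, the variance falls by 15% to 35% in completers and by 12% to 30% in the intent-to-treat fit. The true gain is unknown and could be close to nil at a high correlation combined with a larger follow-up SD.

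The exact identity with mean change needs complete data and a linear link. Under a count link for heavy episodic drinking it would not be exact. If treatment history took in treatment received after randomisation, unbiasedness could fail, so its definition needs to be settled.

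**What to change.** For each outcome analysed on a linear scale, make the primary model a repeated-measures model with baseline means constrained equal across arms:

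- terms for time and condition x time, with no condition main effect;
- an unstructured 2 x 2 covariance;
- baseline treatment history and its interaction with time;
- women with baseline data only kept in the likelihood;
- the adjusted 3-month difference reported as the effect.

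For the completer analysis, regress the 3-month value on condition, baseline value and baseline treatment history. If a count model is used for heavy episodic drinking frequency, include the baseline count as a covariate. State the link for every outcome and define treatment history as a baseline variable.

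The cost is SAP wording, one re-specified model per outcome and a few degrees of freedom. If outcome data have already been analysed, present the adjusted model as an added analysis and label it so.

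### Does the plan need a scoring rule for drinks per drinking day when a week contains no drinking?

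*Combined protocol and SAP*

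**What the plan says.** Primary Analyses sets out "separate multilevel mixed-effects models for PTSD symptom severity, average drinks per drinking day, heavy episodic drinking frequency, and alcohol consequences" from baseline to 3 months. It then repeats the approach at seven waves for three of these outcomes, to examine "differences between BRITE and AO in PTSD symptom severity, average drinks per drinking day, and heavy episodic drinking frequency using self-reports at baseline" and at the later waves. Both sets are random-intercept models that test condition by time.

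Under Measures, the weekly drinking instrument is the DDQ, used "to assess quantity/frequency of alcohol use over the previous week". The interview measure (TLFB) covers the prior month. Eligibility is also monthly: "Participants will endorse hazardous drinking over the past month".

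The one sentence on scoring, in the Data analytic plan, is that "scale scores will be calculated for each of the variables following previously validated procedures". The Missing data section deals with drop-out and with partly completed data: "For missing data due to a participant providing incomplete data, we will examine whether the missingness can be considered ignorable". Neither says what to do with a fully completed questionnaire that reports no drinking.

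**The concern.** The outcome is a ratio, total drinks over drinking days, and it is 0/0 in a dry window. Because entry is judged over a month and the DDQ covers a week, a dry week is possible even at baseline. It becomes more likely afterwards if the intervention reduces drinking, so dry weeks could be more common in one arm.

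Two scorings then suggest themselves. If dry weeks are missing, the outcome describes amount on the occasions when women drank. If they are coded 0, less frequent drinking shows up as less drinking per occasion. Two analysts could report different results from the same data. With about 30 women per arm, a handful of dry weeks carries weight.

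**Working it through.** **Inputs from the documents.** Windows of 7 days (DDQ) and about 30 days (TLFB); seven waves; a random-intercept model; 38 women per arm, with "bonus payments for full completion to achieve an expected 80% retention rate", so 38 x 0.80 = 30.4, or about 30 per arm. The documents give no figure for dry weeks, so there is none to reproduce.

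**Assumed inputs.** Share of days with drinking *p*, share of abstinent women *a*, and 5 drinks per drinking day on average, unchanged in both arms.

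**Step 1: how often the ratio is undefined.** With independent days, the dry share is a + (1 - a)(1 - p)^n. For n = 7:

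- AO, p = 0.30, a = 0.05: 0.05 + 0.95 x 0.0824 = 12.8%, or 3.8 of 30 women.
- Intervention, p = 0.20, a = 0.15: 0.15 + 0.85 x 0.2097 = 32.8%, or 9.8 of 30 women.

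If *p* varies substantially between women (beta distribution, concentration 4), the shares are 26.7% and 48.1%. Among women with any drinking in the past 30 days, the baseline DDQ is dry for 8.2% (constant *p* = 0.30) to 18.4% (varying *p*).

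For the TLFB (n = 30), 0.70^30 and 0.80^30 are 0.0% and 0.1%, so only abstinence matters: 5.0% vs 15.1%, or 10.1% vs 27.8% with between-woman variation. This affects the 3-month wave only, because entry requires drinking in the past month.

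**Step 2: what coding 0 would do.** With amount unchanged, the spurious difference is -5 x (difference in dry shares). The planned seven-wave model was also simulated with 30 women per arm, taking the 3-month minus baseline contrast (2,000 trials in the first row, 500 in the others; the first-row estimate comes from a sample of 40,000 per arm).

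| AO vs intervention (assumed) | Dry share | 5 x difference | Simulated estimate, coded 0 | Significant, coded 0 | Significant, missing |
|---|---|---|---|---|---|
| Days 30% vs 20%, abstinent 5% vs 15% | 12.8% vs 32.8% | 1.00 | -0.99 | 24% | 7% |
| Days 30% vs 20%, none abstinent | 8.2% vs 21.0% | 0.64 | -0.64 | 12% | 6% |
| Days 30% vs 25%, abstinent 5% vs 10% | 12.8% vs 22.0% | 0.46 | -0.47 | 11% | 7% |
| Days 40% vs 35%, abstinent 5% vs 8% | 7.7% vs 12.5% | 0.24 | -0.21 | 8% | 4% |
| Equal arms | equal | 0 | - | 6% | 7% |

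The one-drink effect is therefore the strong case, and it disappears when the arms have equal dry shares. The same arithmetic for the TLFB in the first scenario gives 5 x (0.151 - 0.050) = 0.50.

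**Step 3: what leaving the ratio missing does.** In the first scenario the estimate is 0.01. If only lighter drinkers abstain it is +0.06 (5% significant), and if only heavier drinkers abstain it is -0.06 (5%). With frequency varying between women it is -0.04 (5%). The bias from modelling only the weeks with drinking is small here.

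**Step 4: when amount truly changes.** Suppose 10% vs 30% of women cut both days and amount, a true difference of -0.40. Left missing gives -0.31 and coded 0 gives -0.58. Missing is off by 0.09 and coded 0 by 0.18.

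**Step 5: different assumptions.** A separate simulation used 4.5 drinks per drinking day, between- and within-woman SDs of 1.5 and 1.8, a joint condition by time test and 150 trials per scenario. With 10% vs 25% dry weeks and no effect, coded 0 gave -0.79 (18% significant) and missing gave -0.04 (3%). With 30% vs 10% dry weeks and a true effect of -1.0, coded 0 gave +0.21 and missing gave -0.80. Simulation error is up to about 4 percentage points, and a few fits gave convergence warnings.

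**The case for a change.** The strongest reply is that silence is not a rule. The scoring sentence names no procedure, and the missing-data section applies only once someone has decided that a dry week counts as missing, which is the open question. The Power analysis says the trial was sized for efficacy on drinking as well as PTSD, so its pilot status does not excuse the gap. In the separate simulation the two scorings disagreed on significance in 19% to 47% of trials wherever dry shares differed or a true effect existed.

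The silence does stand, as does the point that the two scorings measure different things. A result on drinks per drinking day describes weeks with drinking, not all weeks of all randomised women. What does not stand is the step from silence to harm. Every large discrepancy needs an analyst to add a recode to 0 that the plan nowhere mentions and that contradicts the name of the measure. A written rule would only record the reading that the arithmetic already gives. Whether the validated procedures cover dry weeks cannot be checked from the documents.

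Adding total drinks as an outcome is a preference, not a repair. Heavy episodic drinking frequency is already in both sets of models. In the strong scenario, expected drinking days are 0.95 x 0.30 = 0.285 vs 0.85 x 0.20 = 0.170 per day, a ratio of 0.60, and with amount per occasion unchanged heavy episodes fall by the same 40%. Loss of lighter days alone would escape that measure, but that concerns the choice of outcomes, not the scoring of a dry week.

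**Conclusion.** The omission is real, but it is a gap that analysts fill sensibly. Without a recode, 0/0 enters the planned Stata model as a missing observation, and the woman's other waves are kept. On that reading, with no true change in amount, the simulated estimates lie within 0.1 drinks of zero and 3% to 7% of trials are significant. Where amount does change, the shortfalls seen are -0.31 against -0.40 and, in the small separate simulation, -0.80 against -1.0. The distortion of about -0.2 to -1.0 drinks (Step 2) belongs to a coding that the plan does not specify, and its size depends on between-arm differences in dry weeks that the documents do not give. The month-long TLFB model is much less exposed. Reporting how many women had dry windows beside the estimate is ordinary good practice and needs no amendment.
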